8.4.5.2 Patient’s global assessment

The patient’s global assessment of disease activity will be performed using 100 mm VAS ranging from no disease activity to maximal disease activity, after the question on how well the patient is doing with the disease considering all aspects affected by the disease.

The investigator will then measure the distance in mm from the left edge of the scale and the value will be entered on the eCRF.

8.4.6 Patient-Reported Outcome

Refer to [Section 8.4.1](#), [Section 8.4.2](#), [Section 8.4.3](#) and [Section 8.4.4](#) for patient-reported Outcome.

The patients will be asked to complete a paper copy of the questionnaires or VAS scale in their local language. The printed copy will serve as source data and the patients’ responses will be transcribed into the eCRF.

Completed questionnaires and VAS scale will be reviewed and examined by the Investigator before the clinical examination for responses which may indicate potential AEs or SAEs. The Investigator should review not only the responses to the VAS scale, but also for any unsolicited comments written by the patient.

If the occurrence of AEs or SAEs is confirmed, the Investigator should record the events as per instructions given in [Section 9](#) Investigators should not encourage the patients to change the responses reported on the VAS scale.

Corporate Confidential Information

8.5 Safety

8.5.1 Physical examination

A complete physical examination will include the examination of general appearance, skin, neck (including thyroid), eyes, ears, nose, throat, lungs, heart, abdomen, back, lymph nodes, extremities, vascular and neurological. If indicated based on medical history and/or symptoms, rectal, external genitalia, breast, and/or pelvic exams may be performed.

Information for all physical examinations must be included in the source documentation at the study site and will not be recorded in the CRF. Significant findings that are present prior to informed consent are included in the Relevant Medical History CRF. Significant findings observed after informed consent signature which meet the definition of an Adverse Event must be appropriately recorded on the Adverse Event CRF.

8.5.2 Vital signs

Vital signs include blood pressure (BP), pulse measurements, and body temperature.

After the patient has been sitting for 3 minutes, with back supported and both feet placed on the floor, systolic and diastolic BP will be measured using an automated validated device.

The body temperature will be measured as indicated in the [Assessment schedule](#) according to local regulations. The measurement will be conducted at the same anatomical location throughout the study participation.

8.5.3 Height and weight

Height in centimeters (cm) and body weight, to the nearest 0.1 kilogram [kg] in indoor clothing, but without shoes, will be measured.

Body mass index (BMI) will be calculated using the following formula:

- $BMI = \text{Body weight (kg)} / [\text{Height (m)}]^2$.

8.5.4 Laboratory evaluations

A central laboratory will be used in this study. Central laboratory information, including collection, shipment of samples and reporting of results, may be found in the laboratory manual.

In the case of a laboratory assessment that is listed in the eligibility criteria is **outside of a protocol-specified range** at screening and/or at the baseline visit, the assessment may be repeated once prior to randomization. If the repeat value remains outside of protocol-specified ranges, the patient is excluded from the study.

In the case of a laboratory range is **not specified by the protocol**, but the laboratory is outside the reference range at screening and/or baseline visit, a decision regarding whether the result is of clinical significance or not shall be made by the Investigator, and shall be based, in part, upon the nature and degree of the observed abnormality. The assessment may be repeated once prior to randomization.

In all cases, the Investigator must document in the source documents the clinical considerations (i.e., result was/was not clinically significant and/or medically relevant) in allowing or disallowing the patient to continue in the study.

Clinically relevant deviations of laboratory test results occurring during or at completion of the study must be reported and discussed with Novartis personnel. The results should be evaluated for criteria defining an adverse event and reported as such if the criteria are met. Repeated evaluations are mandatory until normalization of the result(s) or until the change is no longer clinically relevant. In case of doubt, Novartis personnel should again be contacted.

8.5.4.1 Hematology

Hemoglobin, hematocrit, red blood cell count, white blood cell count with differential (e.g., neutrophils, basophils, eosinophils, monocytes, lymphocytes) and platelet count will be measured.

8.5.4.2 Clinical chemistry

Albumin, alkaline phosphatase, total bilirubin, bicarbonate/CO₂, calcium, cholesterol, chloride, creatinine, CK, hsCRP, gamma-GT, glucose, LDH, inorganic phosphorus, lipase, amylase, magnesium, potassium, total protein, AST, ALT, sodium, triglycerides, TSH, T₃, T₄, urea/BUN and uric acid will be measured.

If the total bilirubin concentration is increased above 1.5 times the upper limit of normal, direct and indirect reacting bilirubin should be differentiated.

8.5.4.3 Urinalysis

Dipstick urine tests will be performed measuring leucocytes, nitrite, pH, protein, glucose, ketones, urobilinogen, bilirubin, blood/ hemoglobin.

If the dipstick result is positive for protein, nitrite, leucocytes and/or blood, the sample will be sent for microscopic analysis of WBC, RBC and casts to the central or local laboratory.

8.5.4.8 Electrocardiogram (ECG)

ECGs are assessed to ensure patient safety. Details of all procedures relating to ECG collection and reporting will be described in the SOM. The following measurements will be reported:

- PR interval, QRS duration, heart rate, RR, QT, QTc

The Fridericia QT correction formula (QTcF) should be used for clinical decisions.

Clinically significant abnormalities should be recorded on the relevant section of the medical history/Current medical conditions/AE eCRF page as appropriate.

8.5.5 Pregnancy and assessments of fertility

All pre-menopausal women who are not surgically sterile will have regular pregnancy tests during the study.

Serum pregnancy tests will be performed at screening, baseline and at the End of Study. At all other times urine pregnancy tests may be used.

If a urine pregnancy test is performed and is found to be positive, this will require immediate interruption of the study drug, until a serum β -hCG is performed, and found to be negative. If positive, the patient must be discontinued from the study medication.

When performed at screening and at baseline, the result must be received before the patient may be dosed.

8.5.6 Other safety evaluations

8.5.6.1 Infections

All occurrences of infections must be carefully monitored by the investigator (see also [Section 9.3](#)).

8.6 Pharmacokinetics

PK samples will be collected at the timepoints defined in the [Assessment schedule](#).

In order to better define the PK profile, the timing of the PK sample collection may be altered based on emergent data. The number of samples/blood draws and total blood volume collected will not exceed those stated in the protocol.

Further details on sample collection, numbering, processing and shipment can be found in the Site Operations Manual.

Pharmacokinetic (PK) samples will be obtained and evaluated in all patients.

Corporate Confidential Information

PK samples remaining after completion of the determination of parent may be used for exploratory assessment of metabolites or other bioanalytical purposes (e.g. cross check between different sites, stability assessment). **Corporate Confidential Information**

For standard pharmacokinetic abbreviations and definitions see the list provided at the beginning of this protocol.

Corporate Confidential Information

PK parameters will be calculated as per Novartis Guidance on Standardization of Pharmacokinetic Parameters. **Corporate Confidential Information**

8.7 Other assessments

Corporate Confidential Information

Corporate Confidential Information

Corporate Confidential Information

Corporate Confidential Information

Corporate Confidential Information

Corporate Confidential Information

9 Safety monitoring

9.1 Adverse events

An adverse event (AE) is any untoward medical occurrence (i.e., any unfavorable and unintended sign [including abnormal laboratory findings], symptom or disease) in a patient or clinical investigation patient *after providing written informed consent* for participation in the study. Therefore, an AE may or may not be temporally or causally associated with the use of a medicinal (investigational) product.

The occurrence of adverse events should be sought by non-directive questioning of the patient at each visit during the study. Adverse events also may be detected when they are volunteered by the patient during or between visits or through physical examination, laboratory test, or other assessments.

Abnormal laboratory values or test results constitute adverse events only if they fulfill at least one of the following criteria:

- they induce clinical signs or symptoms,
- they are considered clinically significant,
- they require therapy.

Clinically significant abnormal laboratory values or test results should be identified through a review of values outside of normal ranges/clinically notable ranges, significant changes from baseline or the previous visit, or values which are considered to be non-typical in patients with underlying disease. Investigators have the responsibility for managing the safety of individual patient and identifying adverse events. Alert ranges for liver related events are included in [Section 9.4](#).

Adverse events must be recorded on the Adverse Events CRF for patients that pass screening and enter into the study. The adverse events should be reported according to the signs, symptoms or diagnosis associated with them, and accompanied by the following information:

1. the Common Toxicity Criteria (CTC) AE grade (version 4.03)
If CTC-AE grading does not exist for an adverse event, use:
1=mild,

2=moderate,

3=severe

4=life threatening* (see [Section 9.2](#) for definition of a serious adverse event (SAE))

*Note: There may be cases where a CTCAE with a grade of 4 (life-threatening) may not necessarily be an SAE (e.g. certain laboratory abnormalities in the absence of meeting other seriousness criteria).

CTC-AE grade 5 (death) is not used, but is collected in other CRFs (e.g. Study Completion, Death/Survival).

2. its relationship to the study treatment (no/yes).
3. its duration (start and end dates) or if the event is ongoing at the end of study.
4. whether it constitutes a serious adverse event (SAE) See [Section 9.2](#) for definition of SAE
5. action taken regarding investigational treatment.

All adverse events must be treated appropriately. Treatment may include one or more of the following:

- no action taken (e.g. further observation only)
 - investigational treatment dosage increased/reduced
 - investigational treatment interrupted/withdrawn
 - concomitant medication or non-drug therapy given
 - hospitalization/prolonged hospitalization (see [Section 9.2](#) for definition of SAE)
6. its outcome (not recovered/not resolved; recovered/resolved; recovering/resolving, recovered/resolved with sequelae; fatal; or unknown).

Information about common side effects already known about the investigational drug can be found in the Investigator's Brochure (IB). Once an adverse event is detected, it should be followed until its resolution or until it is judged to be permanent, and assessment should be made at each visit (or more frequently, if necessary) of any changes in severity, the suspected relationship to the study drug, the interventions required to treat it, and the outcome.

The investigator should also instruct each patient to report any new adverse event (beyond the protocol observation period) that the patient, or the patient's personal physician, believes might reasonably be related to study treatment. This information should be recorded in the investigator's source documents, however, if the AE meets the criteria of an SAE, it must be reported to Novartis.

9.2 Serious adverse event reporting

9.2.1 Definition of SAE

An SAE is defined as any adverse event (appearance of (or worsening of any pre-existing) undesirable sign(s), symptom(s) or medical conditions(s) which meets any one of the following criteria:

- is fatal or life-threatening
- results in persistent or significant disability/incapacity

- constitutes a congenital anomaly/birth defect
- requires inpatient hospitalization or prolongation of existing hospitalization, unless hospitalization is for:
 - routine treatment or monitoring of the studied indication, not associated with any deterioration in condition
 - elective or pre-planned treatment for a pre-existing condition that is unrelated to the indication under study and has not worsened since the start of study drug
 - treatment on an emergency outpatient basis for an event not fulfilling any of the definitions of a SAE given above and not resulting in hospital admission
 - social reasons and respite care in the absence of any deterioration in the patient's general condition
- is medically significant, i.e. defined as an event that jeopardizes the patient or may require medical or surgical intervention.

Life-threatening in the context of a SAE refers to a reaction in which the patient was at risk of death at the time of the reaction; it does not refer to a reaction that hypothetically might have caused death if more severe.

All malignant neoplasms will be assessed as serious under “medically significant” if other seriousness criteria are not met.

Any suspected transmission via a medicinal product of an infectious agent is also considered a serious adverse reaction.

Medical and scientific judgment should be exercised in deciding whether other situations should be considered serious reactions, such as important medical events that might not be immediately life threatening or result in death or hospitalization but might jeopardize the patient or might require intervention to prevent one of the other outcomes listed above. Examples of such events are intensive treatment in an emergency room or at home for allergic bronchospasm, blood dyscrasias or convulsions that do not result in hospitalization or development of dependency or abuse.

Any suspected transmission via a medicinal product of an infectious agent is also considered a serious adverse reaction.

All AEs (serious and non-serious) are captured on the CRF, SAEs also require individual reporting to DS&E as per [Section 9.2.2](#).

9.2.2 SAE reporting

To ensure patient safety, every SAE, regardless of causality, occurring after the patient has provided informed consent and until 30 days following the last administration of study treatment must be reported to Novartis within 24 hours of learning of its occurrence as described below. Any SAEs experienced after this should only be reported to Novartis if the investigator suspects a causal relationship to study treatment.

Note: SAEs reported by subjects deemed to be screen failures must be reported to Novartis as outlined here with appropriate information also captured in the CRFs as specified in the Site Operations Manual.

Recurrent episodes, complications, or progression of the initial SAE must be reported as follow-up to the original episode, regardless of when the event occurs. This report must be submitted within 24 hours of the investigator receiving the follow-up information. An SAE that is considered completely unrelated to a previously reported one should be reported separately as a new event.

Information about all SAEs (either initial or follow up information) is collected and recorded on the paper Serious Adverse Event Report Form. The investigator must assess the relationship to each specific component of study treatment (if study treatment consists of several drugs) complete the SAE Report Form in English, and send the completed, signed form by fax within 24 hours after awareness of the SAE to the local Novartis Drug Safety and Epidemiology Department, notifying the Clinical Trial Leader. Contact information is listed in the Site Operations Manual.

The original copy of the SAE Report Form and the fax confirmation sheet must be kept with the source documentation at the study site. Follow-up information should be provided using a new paper SAE Report Form stating that this is a follow-up to a previously reported SAE.

Follow-up information provided should describe whether the event has resolved or continues, if and how it was treated, whether the treatment code was broken or not and whether the subject continued or withdrew from study participation. Each re-occurrence, complication, or progression of the original event should be reported as a follow-up to that event regardless of when it occurs.

If the SAE is not previously documented in the Investigator's Brochure or Package Insert (new occurrence) and is thought to be related to the investigational treatment a Drug Safety and Epidemiology Department associate may urgently require further information from the investigator for Health Authority reporting. Novartis may need to issue an Investigator Notification (IN) to inform all investigators involved in any study with the same investigational treatment that this SAE has been reported. Suspected Unexpected Serious Adverse Reactions (SUSARs) will be collected and reported to the competent authorities and relevant ethics committees in accordance with EU Guidance 2011/C 172/01 or as per national regulatory requirements in participating countries.

Follow the detailed instructions outlined in the Site Operations Manual regarding the submission process for reporting SAEs to Novartis.

Note: SAEs must be reported to Novartis within 24 hours of the investigator learning of its occurrence/receiving follow-up information.

9.3 Infection Monitoring

All infections that develop during the study will be reported as AEs. Investigators are requested to specifically ask about infections at each visit, in particular bacterial enterocolitis. Treatment and additional evaluations will be performed at the discretion of the investigator. The investigator should consider early treatment with specific antimicrobial therapy on the basis of clinical diagnosis or suspicion thereof in consultation with infectious disease experts, as appropriate.

WBC will be assessed at every visit. If the neutrophil count falls below 1000 per μl , then weekly assessments of WBC are recommended.

The investigator should remind the patient of the risk of infections and to instruct them to promptly report any symptoms of infections to the investigator.

9.4 Liver safety monitoring

To ensure patient safety and enhance reliability in determining the hepatotoxic potential of an investigational drug, a standardized process for identification, monitoring and evaluation of liver events has to be followed.

The following two categories of abnormalities / adverse events have to be considered during the course of the study:

- Liver laboratory triggers, which will require repeated assessments of the abnormal laboratory parameter
- Liver events, which will require close observation, follow-up monitoring and completion of the standard base liver CRF pages

Please refer to [Table 9-1](#) and [Table 9-2](#) for complete definitions of liver laboratory triggers and liver events.

Every liver laboratory trigger or liver event should be followed up by the investigator or designated personal at the trial site, as summarized below and detailed in [Table 9-2](#).

For the liver laboratory trigger:

- Repeating the LFT within the next week to confirm elevation.

These LFT repeats should be performed using the central laboratory if possible. If this is not possible, then the repeats can be performed at a local laboratory to monitor the safety of the patient. Repeats laboratory should then be performed at central laboratory as soon as possible. If a liver event is subsequently reported, any local LFTs previously conducted that are associated with this event should be reported on the Liver CRF pages.

- If the elevation is confirmed, close observation of the patient will be initiated, including consideration of treatment interruption if deemed appropriate.

For the liver events:

- Repeating the LFT to confirm elevation as appropriate
- Discontinuation of the investigational drug (refer to [Section 7.1](#), if appropriate)
- Hospitalization of the patient if appropriate
- A causality assessment of the liver event via exclusion of alternative causes (e.g. disease, co-medications)
- An investigation of the liver event which needs to be followed until resolution.

These investigations can include serology tests, imaging and pathology assessments, hepatologist's consultancy, based on investigator's discretion. All follow-up information, and

the procedures performed should be recorded as appropriate in the CRF, including the liver event overview CRF pages.

Table 9-1 Liver Event and Laboratory Trigger Definitions

| | Definition/ threshold |
|---------------------------|---|
| Liver laboratory triggers | 
 • $3 \times \text{ULN} < \text{ALT} / \text{AST} \leq 5 \times \text{ULN}$ • $1.5 \times \text{ULN} < \text{TBL} \leq 2 \times \text{ULN}$ |
| Liver events | 
 • $\text{ALT or AST} > 5 \times \text{ULN}$ • $\text{ALP} > 2 \times \text{ULN}$ (in the absence of known bone pathology) • $\text{TBL} > 2 \times \text{ULN}$ (in the absence of known Gilbert syndrome) • $\text{ALT or AST} > 3 \times \text{ULN}$ and $\text{INR} > 1.5$ • Potential Hy's Law cases (defined as $\text{ALT or AST} > 3 \times \text{ULN}$ and $\text{TBL} > 2 \times \text{ULN}$ [mainly conjugated fraction] without notable increase in ALP to $> 2 \times \text{ULN}$) • Any clinical event of jaundice (or equivalent term) • $\text{ALT or AST} > 3 \times \text{ULN}$ accompanied by (general) malaise, fatigue, abdominal pain, nausea, or vomiting, or rash with eosinophilia • Any adverse event potentially indicative of a liver toxicity * |

Table 9-2 Follow Up Requirements for Liver Events and Laboratory Triggers

| Criteria | Actions required | Follow-up monitoring |
|--|---|--|
| Potential Hy's Law case ^a | 
 Discontinue the study drug immediately Hospitalize, if clinically appropriate Establish causality Complete liver CRF | ALT, AST, TBL, Alb, PT/INR, ALP and γ GT until resolution ^c (frequency at investigator discretion) |
| ALT or AST | | |
| > 8 × ULN | 
 Discontinue the study drug immediately Hospitalize if clinically appropriate Establish causality Complete liver CRF | ALT, AST, TBL, Alb, PT/INR, ALP and γ GT until resolution ^c (frequency at investigator discretion) |
| > 3 × ULN and INR > 1.5 | 
 Discontinue the study drug immediately Hospitalize, if clinically appropriate Establish causality Complete liver CRF | ALT, AST, TBL, Alb, PT/INR, ALP and γ GT until resolution ^c (frequency at investigator discretion) |
| > 5 to ≤ 8 × ULN | 
 Repeat LFT within 48 hours If elevation persists, continue follow-up monitoring If elevation persists for more than 2 weeks, discontinue the study drug Establish causality Complete liver CRF | ALT, AST, TBL, Alb, PT/INR, ALP and γ GT until resolution ^c (frequency at investigator discretion) |
| > 3 × ULN accompanied by symptoms ^b | 
 Discontinue the study drug immediately Hospitalize if clinically appropriate Establish causality Complete liver CRF | ALT, AST, TBL, Alb, PT/INR, ALP and γ GT until resolution ^c (frequency at investigator discretion) |
| > 3 to ≤ 5 × ULN (patient is asymptomatic) | 
 Repeat LFT within the next week If elevation is confirmed, initiate close observation of the patient | Investigator discretion Monitor LFT within 1 to 4 weeks |
| ALP (isolated) | | |
| > 2 × ULN (in the absence of known bone pathology) | 
 Repeat LFT within 48 hours If elevation persists, establish causality Complete liver CRF | Investigator discretion Monitor LFT within 1 to 4 weeks or at next visit |

| Criteria | Actions required | Follow-up monitoring |
|--|---|---|
| TBL (isolated) | | |
| > 2 × ULN (in the absence of known Gilbert syndrome) | 
 Repeat LFT within 48 hours If elevation persists, discontinue the study drug immediately Hospitalize if clinically appropriate Establish causality Complete liver CRF | ALT, AST, TBL, Alb, PT/INR, ALP and γGT until resolution ^c (frequency at investigator discretion) Test for hemolysis (e.g. reticulocytes, haptoglobin, unconjugated [indirect] bilirubin) |
| > 1.5 to ≤ 2 × ULN (patient is asymptomatic) | 
 Repeat LFT within the next week If elevation is confirmed, initiate close observation of the patient | Investigator discretion Monitor LFT within 1 to 4 weeks or at next visit |
| Jaundice | 
 Discontinue the study drug immediately Hospitalize the patient Establish causality Complete liver CRF | ALT, AST, TBL, Alb, PT/INR, ALP and γGT until resolution ^c (frequency at investigator discretion) |
| Any AE potentially indicative of a liver toxicity* | 
 Consider study drug interruption or discontinuation Hospitalization if clinically appropriate Establish causality Complete liver CRF | Investigator discretion |

*These events cover the following: hepatic failure, fibrosis and cirrhosis, and other liver damage-related conditions; the non-infectious hepatitis; the benign, malignant and unspecified liver neoplasms

^aElevated ALT/AST > 3 × ULN and TBL > 2 × ULN but without notable increase in ALP to > 2 × ULN

^b(General) malaise, fatigue, abdominal pain, nausea, or vomiting, or rash with eosinophilia

^cResolution is defined as an outcome of one of the following: (1) return to baseline values, (2) stable values at three subsequent monitoring visits at least 2 weeks apart, (3) remain at elevated level after a maximum of 6 months, (4) liver transplantation, and (5) death.

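### Table 9-2 sets a weaker mandatory action for ALT/AST >3 to ≤8 × ULN with TBL and ALP both >2 × ULN (asymptomatic, INR ≤1.5, no jaundice) than for TBL >2 × ULN alone

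*Protocol*

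**What the plan says.** All references are to Protocol Section 9.4 unless stated otherwise.

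- **Hy's Law row.** The study drug is stopped immediately. Footnote a defines the case as ALT/AST >3 × ULN "and TBL > 2 × ULN but without notable increase in ALP to > 2 × ULN". Table 9-1 carries the same ALP exclusion.
- **TBL >2 × ULN, under a heading restricted to isolated rises.** Liver tests are repeated within 48 hours, then: "If elevation persists, discontinue the study drug immediately". Known Gilbert syndrome is excepted.
- **ALP >2 × ULN, also headed as isolated.** Repeat within 48 hours and establish causality. No stop is stated.
- **ALT/AST >3 to ≤5 × ULN, asymptomatic.** "Repeat LFT within the next week If elevation is confirmed, initiate close observation of the patient".
- **ALT/AST >5 to ≤8 × ULN.** Repeat within 48 hours, then "If elevation persists, continue follow-up monitoring". A stop is required only once the elevation has lasted more than 2 weeks.
- **Other immediate-stop rows.** ALT/AST >8 × ULN; ALT/AST >3 × ULN with INR >1.5; ALT/AST >3 × ULN with symptoms (footnote b); jaundice.
- **Adverse event potentially indicating liver toxicity.** "Consider study drug interruption or discontinuation".

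Table 9-1 lists TBL >2 × ULN and ALP >2 × ULN as liver events in their own right. The combined case therefore still comes under the general text: "Liver events, which will require close observation, follow-up monitoring and completion of the standard base liver CRF pages". That text also calls for a causality assessment and follow-up to resolution. It lists discontinuation with a reference to Section 7.1, qualified as applying where appropriate.

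**The concern.** A liver stopping table should not become more lenient as the picture worsens. Here, a patient with raised bilirubin who also has raised transaminases and raised ALP moves from a row with a mandatory stop on persistence to rows with a late stop or none. The visible text gives no reason for this. Keeping high ALP out of the Hy's Law label is a classification choice, but the table supplies no substitute action for the cases it excludes.

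Safety and tolerability form a primary objective (Section 2.1), and Section 10.4 says no data monitoring committee is required. For this profile, whether the drug is stopped rests on the individual investigator, although Section 9.4 sets out to standardize liver handling. The point concerns patient handling only. Recording, causality assessment and follow-up are covered, and no efficacy analysis is touched.

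**Working it through.** The plan gives no figure to reproduce. The check applies the Table 9-2 thresholds row by row.

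**Inputs.** Row definitions and actions come from Tables 9-1 and 9-2 with footnotes a and b. The dose is 70 mg b.i.d. (Section 6.2). Known Gilbert syndrome and bone pathology are assumed absent, and isolated is read literally, meaning the other liver tests are not also raised.

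**Step 1: test cases** (multiples of ULN; INR 1.0, no jaundice)

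| ALT/AST | TBL | ALP | Symptoms | Matching row | Mandatory action |
|---|---|---|---|---|---|
| 1 | 2.5 | 1 | no | TBL isolated | repeat ≤48 h; stop if it persists |
| 4 | 2.5 | 1 | no | Hy's Law (and ALT/AST >3 to ≤5) | immediate stop |
| 4 | 2.5 | 2.5 | no | ALT/AST >3 to ≤5 | repeat ≤1 week; observe |
| 7 | 2.5 | 2.5 | no | ALT/AST >5 to ≤8 | repeat ≤48 h; stop only if >2 weeks |
| 4 | 2.5 | 2.5 | yes | ALT/AST >3 with symptoms | immediate stop |

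Lines 3 and 4 carry a weaker mandatory action than line 1. There is also a cliff: at ALT 4 × and TBL 2.5 ×, ALP of 2.0 × means an immediate stop, while ALP of 2.1 × means a repeat within a week.

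**Step 2: how wide the gap is.** Fix TBL >2 × and ALP >2 × ULN. Vary ALT/AST (>3 to ≤5, >5 to ≤8, >8), INR (≤1.5, >1.5), symptoms (no, yes) and jaundice (no, yes).

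- Profiles: 3 × 2 × 2 × 2 = 24.
- ALT/AST >8 ×: 8 profiles, all immediate stop.
- The two lower bands: 16 profiles. In each band, only one of 8 has INR ≤1.5, no symptoms and no jaundice, so 2 do not reach an immediate stop and 14 do.
- Total with an immediate stop: 8 + 14 = 22. Not reached: 2.

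These are counts of profiles, not probabilities.

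**Step 3: difference between mandatory deadlines**, compared with isolated TBL >2 × ULN and ignoring laboratory turnaround.

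- ALT/AST >5 to ≤8 ×: more than 14 days against 2 days. 14 − 2 = 12 days at least; 12 × 2 = 24 doses; 24 × 70 mg = 1,680 mg.
- ALT/AST >3 to ≤5 ×: the first repeat may come at 7 days against 2. 7 − 2 = 5 days, or 10 doses. No mandatory stop follows, and the follow-up column then allows liver tests at 1 to 4 weeks.

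**Step 4: is the stop restored elsewhere?** Section 9.4 qualifies discontinuation for liver events as above. The mandatory list in Section 7.1 has no liver threshold. It does require a stop for a drug-related serious adverse event, or when the investigator believes continuing would be detrimental, but both depend on judgement. The liver-toxicity adverse event row only asks that a stop be considered. No mandatory laboratory-based stop is restored.

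**Step 5: effect of the fix.** If the TBL >2 × ULN row applies whether or not the rise is isolated, lines 3 and 4 of the table both gain a repeat within 48 hours and a stop on persistence. The inversion disappears.

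**The case against.** The strongest reply is that everything turns on one heading word. Table 9-1 makes TBL >2 × ULN a liver event without calling it isolated, and Section 9.4 points to Table 9-2 for the detail. A site could reasonably match the event to the TBL >2 × row, and the problem would vanish. That reading is workable, but the heading says otherwise, and nothing in the protocol says to combine rows or to apply the strictest one.

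A second argument is that the lower band borrows the row for a laboratory trigger, whereas the combined case is a liver event for which Section 9.4 lists discontinuation. The qualifier there sits inside the cross-reference bracket and might modify only the reference. But if discontinuation were unconditional for every liver event, it would contradict Table 9-2's own >5 to ≤8 × row, which lets treatment continue for up to 2 weeks.

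Third, footnote b lists fatigue without requiring it to be new. Section 1.1 reports fatigue in as many as 85% of patients, and entry requires ESSPRI ≥5, with fatigue as one of its three areas. If pre-existing fatigue counts, many of these cases reach the immediate-stop row. This stands as a real narrowing, but the protocol does not say whether it counts.

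Two further points stand. The 12 days and 24 doses are differences between mandatory deadlines, not expected extra exposure: an investigator may stop on the first day, and worsening to ALT/AST >8 × or INR >1.5 triggers an immediate stop. Also, with about 18 patients planned on CDZ173 for 12 weeks, the case may never arise.

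**Conclusion.** The concern holds. On the table as written, two profiles (ALT/AST >3 to ≤5 × and >5 to ≤8 × ULN, each with TBL >2 × and ALP >2 × ULN, INR ≤1.5, no listed symptom, no jaundice) carry a weaker mandatory action than TBL >2 × ULN alone. In the higher band the compulsory stop is at least 12 days later. In the lower band there is none.

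This rests on reading isolated literally, on no known Gilbert syndrome, and on the patient being counted as asymptomatic. How often it would occur cannot be derived from the documents. It is a narrow inconsistency in patient handling, worth correcting because the remedy is only wording.

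**What to change.** Delete the word isolated from the heading of the TBL >2 × ULN row. Alternatively, add a row for ALT/AST >3 × with TBL >2 × and ALP >2 × ULN, with action at least as strong as the TBL row: repeat within 48 hours and discontinue if it persists. In either case, state that the strictest matching row applies. Deleting the word has a small further advantage: TBL and ALP both >2 × ULN with ALT/AST at 1 × ULN, which matches no laboratory row on a literal reading, would then be covered too.

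The cost is a change to table wording. ALT, AST, bilirubin and ALP are already in the chemistry panel (Section 8.5.4.2). The downside is an occasional earlier repeat test or treatment discontinuation.
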